13.6.1. Primary Analysis

The following statistical tests will be done corresponding to the objective listed in section 13.2. The following two summary scores will be calculated per subject for each selected scale:

- the mean changes from baseline during treatment (AC-DT) = the average of all post-baseline scale scores up to and including the end-of-treatment visit minus the score at baseline. Only scores from valid HRQoL forms will be included.

- the mean changes from baseline after treatment (AC-AT): = the average of all post-baseline scale scores during follow-up (ie, after the end-of-treatment visit) minus the score at baseline. Only scores from valid HRQoL forms will be included.

Description of the AC-DT and AC-AT will be presented (mean, standard deviation, median, first and third quartiles, minimum, maximum) by treatment group. The mean difference between the two treatment arms for AC-DT and for AC-AT with corresponding 2-sided 95% CI will be derived and contrasted with the 0 (no treatment arm difference) and the clinically important difference (CID) threshold, as defined in a recently published paper of Cocks et al, 2012. The status change (improved/no change/deteriorated) for the proportion of patients analysis will be defined based on the pre-defined clinically important response (CIR) threshold as recommended by Cocks and Buchanan (2015).

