## 5.3 Treatment duration

In the standard arm, patients will receive up to 6 cycles of TMZ as maintenance at a dose of 150-200 mg/m^2 daily for 5 days every 28 days, unless treatment is discontinued for disease progression, unacceptable toxicity, or withdrawal of consent.

Continuation of maintenance temozolomide beyond 6 cycles (e.g., for a maximum of 12 cycles) is not encouraged but is left to the discretion of the Investigator and the interest of the patient.

In the experimental arm, patients will receive up to 6 cycles of MRZ+TMZ in the maintenance setting, followed by another 12 cycles of MRZ alone, unless treatment is discontinued for disease progression, unacceptable toxicity, withdrawal of consent, or the patient has completed the 18 cycles of MRZ as planned. In the event that one drug (TMZ or MRZ) is discontinued for reasons other than disease progression, the other will then continue as a single agent.

At study closure, all study participants may continue to receive study treatment as planned in the protocol (see chapter 4) provided that they benefit from it and all protocol-specified criteria for continuing study treatment are met. For all patients who discontinue treatment for reasons other than disease progression, whenever possible, tumor assessment will continue as per protocol until disease progression, or start of a new treatment regimen.

After disease progression, treatment will be left to the discretion of the treating physician. Any further anti-cancer therapy will not be considered as part of the protocol treatment. However, patients will be followed for survival and the start of first new anti-GBM therapy and its outcome.

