## 6.3 After the end of treatment (Follow-up)

### 6.3.1 End-of-Treatment Visit

The following assessment should be done ( $28 \pm 7$  days) after the last marizomib or temozolomide dosing (whether the patient has progressed or completed the full duration of planned treatment)

- physical examination (weight)
- Karnofsky Performance Status (KPS) scale (Appendix E)
- vital signs (heart rate, temperature, blood pressure)
- concomitant medications and procedures
- adverse events
- hematology as in section 6.1
- biochemistry as in section 6.1
- urinalysis as in section 6.1
- For WOCBP, urine or serum pregnancy tests
- brain MRI scan if one has not been done in the previous 4 weeks and no progression as yet been recorded

If patient has stopped treatment due to progression:

- MMSE
- For participating centers, tests of objective neurocognitive function: HVLT-R, Trail Making Tests Part A & B and COWA and the MOS questionnaire on self-perceived neurocognitive function (Appendix J)
- translational research:
  - Mandatory: 10 mL blood draw for plasma and 10 mL blood draw for serum
  - Optional: 10 mL blood draw for extracellular vesicles and 20 mL for PBMC

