5.1. Overall Study Design and Plan

This is a multicenter, randomized, controlled, open-label Phase 3 superiority trial with a safety monitoring plan and an early stopping rule for futility.

After signing the informed consent form and upon confirmation of the subject eligibility, subjects were randomized 1:1 to the experimental arm, referred to as (MRZ/TMZ/RT)→MRZ/TMZ, or to the control arm (TMZ/RT→TMZ). The total targeted number of subjects to be randomized is 750 (approximately 375 in each arm).

Experimental arm: Standard radiotherapy (60 Gy in 30 fractions over 6 weeks) + TMZ 75 mg/m² orally (PO) daily for 6 weeks (during RT) and MRZ dose 0.8 mg/m² intravenously (IV) at days 1, 8, 15, 29 and 36.

This is followed, after 4-week break, by up to 6 cycles of maintenance TMZ 150-200 mg/m² PO on days 1-5 of a 28-day cycle and up to 18 cycles of maintenance MRZ treatment (0.8 mg/m² IV) at days 1, 8, 15 of a 28-day cycle until disease progression, unacceptable toxicity or withdrawal of consent.

Continuation of maintenance TMZ beyond 6 cycles is not encouraged but will not constitute a protocol violation as long as it does not exceed 12 cycles in total.

Control arm: Standard RT (60 Gy in 30 fractions over 6 weeks) + TMZ 75 mg/m² PO daily for 6 weeks (during RT) then (after 4-week break) up to 6 cycles of maintenance TMZ 150-200 mg/m² PO on days 1-5 of a 28-day cycle.

Continuation of maintenance TMZ beyond 6 cycles is not encouraged but will not constitute a protocol violation as long as it does not exceed 12 cycles in total.

Subjects who at the start of the study are planning to get tumor-treating-fields (TTF) treatment are excluded from study entry, however those who decide after completing the concomitant part of the treatment to get TTF as part of their adjuvant treatment will not be discontinued, nor will they be considered protocol violators.

Study treatment was discontinued for a subject in the event of:

- Progressive disease
- Unacceptable overall toxicity for all drugs.
- Protocol violation
- Loss to follow-up
- Patient significant non-compliance
- Pregnancy
- Physician/Patient decision
- Death

An end-of-treatment visit had to be performed, and follow-up for survival, subsequent therapy and date of progressive disease (PD) were collected, whenever feasible.

Subjects had the right to withdraw from the study at any time for any reason.

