13.2. Objective

The main objective of HRQoL assessment within this trial is to determine the impact of addition of MRZ to TMZ and RT therapy on five chosen domains being primarily global HRQoL, with fatigue, physical function, neurocognitive function, communication and motor dysfunction as secondary HRQoL outcomes. It is expected that these are likely to be most affected in subjects, based on the toxicity profiles and information of previous studies. The Ho hypothesis will be tested that there is no difference between subjects in both arms during and after treatment regarding global HRQoL. A secondary objective is to evaluate the effect of the treatment on the remaining symptoms and functioning scales as treatment-related side effects may have a (temporary) negative influence on the health-related domains of HRQoL of these subjects.

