13.6.2. Sensitivity Analysis

The primary analysis will be repeated in the PP and the uMGMT stratum.

The primary analysis will also be repeated taking all received HRQoL forms into account (ie, including invalid/unassigned forms). In addition, two new summary statistics will be created:

- Deterioration during treatment (D10-DT) = A binary variable indicating whether the subject experienced a 10-point decrease from baseline at any post-baseline visit up to and including the end of study treatment visit.
- Deterioration after treatment (D10-AT) = A binary variable indicating whether the subject experienced a 10-point decrease from baseline at any follow-up visit (ie, after the end of study treatment visit).

Description of the D10-DT and D10-AT will be presented (mean, standard deviation, median, first and third quartiles, minimum, maximum) by treatment group together with mean difference, 95% CI to supplement the main analysis.

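### HRQoL scores are cut at each patient's own end of treatment, with planned maintenance of up to 6 v 18 cycles and no time-aligned comparison; D10 counts any 10-point decrease as deterioration

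*SAP*

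**What the plan says.** SAP 13.6.1 forms two scores per patient and scale. AC-DT is "the average of all post-baseline scale scores up to and including the end-of-treatment visit minus the score at baseline"; AC-AT is the same average over forms after that visit. The arms are compared by mean difference with 95% CI, set against zero and a clinically important difference. The section also plans a responder proportion: "The status change (improved/no change/deteriorated) for the proportion of patients analysis will be defined based on the pre-defined clinically important response (CIR) threshold". It gives no time point for it.

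SAP 13.6.2 adds D10-DT, "A binary variable indicating whether the subject experienced a 10-point decrease from baseline at any post-baseline visit" up to end of treatment, and D10-AT for later visits, reported "together with mean difference, 95% CI to supplement the main analysis". Protocol 10.5.1 and 10.5.2 define the same scores.

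Protocol 6.3.1 places the end-of-treatment visit 28 ± 7 days "after the last marizomib or temozolomide dosing (whether the patient has progressed or completed the full duration of planned treatment"). No HRQoL form is listed at that visit, so it acts only as a cut. SAP 5.1 gives control up to 6 maintenance cycles, tolerates 12 temozolomide (TMZ) cycles in either arm, and gives the marizomib (MRZ) arm "up to 18 cycles of maintenance MRZ treatment". If one drug stops for a reason other than progression, protocol 5.3 says that "the other will then continue as a single agent". Forms are due on one calendar in both arms: end of radiotherapy, then every 16 weeks (SAP 13.5).

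The HRQoL null in SAP 13.2 is that "there is no difference between subjects in both arms during and after treatment regarding global HRQoL". The five secondary scales are fatigue, physical function, neurocognitive function, communication and motor dysfunction (SAP 13.6).

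**The concern.** The cut depends on treatment, and planned treatment length differs by arm. During treatment therefore covers different times since randomisation in each arm, and so does after treatment. If HRQoL drifts with time, the averages differ with no drug effect. D10 counts a patient on any one qualifying form, so the arm with more forms in a window has more chances to be counted.

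The other HRQoL analyses do not fill the gap. The per-protocol, uMGMT and all-forms repeats keep the same cut. The trends by dropout pattern in SAP 13.6.3 are a missing-data check. The mixed model with time and time-by-treatment terms (SAP 11.3.3) is for the MMSE only.

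The SAP already records no evidence of a survival benefit and severe neurological and neuropsychiatric toxicity, so HRQoL will be read largely as evidence on harm. From the planned outputs a reader cannot separate a window effect from a drug effect.

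The D10 wording is a second, separate problem. A decrease is deterioration only where higher scores are better, and D10 names no scale.

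**Working it through.** The plan gives no HRQoL power or effect size, so there is no figure of its own to reproduce. The check asks what the planned scores show when marizomib has no effect.

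**Calendar (documents).** Weeks from radiotherapy start: 6 weeks of radiotherapy, a 4-week break, 28-day cycles, end-of-treatment visit 4 weeks after the last dose.
- Control, 6 cycles, last dose day 5: 10 + 5×4 + 4/7 + 4 = week 34.6.
- 12 TMZ cycles: 10 + 11×4 + 4/7 + 4 = week 58.6.
- MRZ, 18 cycles, last dose day 15: 10 + 17×4 + 14/7 + 4 = week 84.

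With forms at weeks 6, 26, 42, 58 and 74, patients completing planned treatment contribute 2, 4 and 5 forms. Counting the 16 weeks from end of radiotherapy instead gives the same counts. The first after-treatment form is at week 42 (control, 6 cycles) or 90 (MRZ).

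**Upper bound, completers only.** With independent risk p per form, P(any drop) = 1 − (1 − p)^k. At p = 0.2: 1 − 0.8² = 36% for 2 forms and 1 − 0.8⁵ = 67% for 5. Most patients stop earlier, so this is not the expected size.

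**All patients.** Assumptions, none given in the documents: the same exponential PFS in both arms (median 7 months), p = 0.2 with independent forms, the window closing at progression or at the weeks above, 6 TMZ cycles, no early stopping, patients with at least one form. Follow-up at cut-off: 286 enrolled by 10 Jul 2019 (protocol 1.1, read as this trial) and 616 by 28 APR 2020, so 330/616 = 54% had under 41.9 weeks. Follow-up is taken as uniform over 0–41.9 weeks for these and 41.9–95 for the rest. For the long-term report, all MRZ is assumed stopped on 14 SEP 2020.
- Control at cut-off: 1.46 forms on average and at most 2, so 0.54 × 20% + 0.46 × 36% = 27.4% (27.3% unrounded).
- MRZ at cut-off: 1.83 forms on average, 31.6%. Excess 31.6 − 27.3 = 4.3 points.
- Long term: about 30% v 36%, an excess of about 5.5 points.

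**D10-AT, same model**, with post-progression survival set so that median OS is the plan's 16 months: about 2 points (cut-off) and 3 points (long term) against control.

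**Varying the D10-DT assumptions (median PFS 7 months, p = 0.2):**

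| Change | Cut-off | Long term |
|---|---|---|
| Within-patient correlation 0.5 | 2.5 | about 3 |
| 40% of MRZ patients stop all drugs before the control window ends | about 1 | about 1 |
| All controls take 12 TMZ cycles, MRZ-arm patients do not | about 0 | 35.7 − 38.9 = −3.2 |
| Both arms take 12 TMZ cycles | about 0 | about 0.5 |

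Over median PFS 5–12 months and p of 10–30%, with or without correlation and stopping of MRZ alone, the excess is 0.7–7.0 points at cut-off and 0.9–9.1 long term. Those ranges leave out TMZ extension and stopping of all drugs. With these included, the range contains zero.

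**AC-DT.** Bias = difference in mean form week / 52.18 × assumed decline per year (5 or 10 points).
- Cut-off: (13.7 − 10.6)/52.18 × 5 or 10 = 0.3 or 0.6.
- Long term: (16.5 − 12.3)/52.18 × 5 or 10 = 0.4 or 0.8, reaching 1.2 at median PFS 12 months and the steeper decline.
- Zero if HRQoL is flat.

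**D10 direction.** SAP 13.3 lists fatigue among the symptom scales and describes the brain-module items as communication deficit and motor dysfunction. If higher means worse on these (inferred from the names; the scoring manuals are not in the documents), a 10-point decrease is an improvement on three of the five secondary scales. The global scale, which is the primary HRQoL endpoint, raises no such problem.

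**The case against.** The strongest reply is that the during/after split is exactly what the stated null asks about, so the scores answer the question posed and a time-aligned model answers another. That stands: AC-DT and AC-AT should be kept, and the gap is one of interpretation.

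A reader might infer that the plan biases HRQoL against marizomib. The documents do not support that. D10-AT moves the other way in the same model. The tolerated TMZ extension can remove or reverse the D10-DT excess. Protocol 5.4 also allows all treatment to stop for toxicity or by physician or patient decision, which shortens the MRZ window. The 36% v 67% contrast for completers is likewise not the size to expect in the trial.

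Three further points are fair. AC-DT, the primary HRQoL analysis, is barely affected. D10 is supplementary, and protocol 10.5 calls HRQoL reporting mainly descriptive and exploratory. SAP section 10 reports treatment duration by arm, so the exposure gap will be visible, though its effect on HRQoL will not. The responder proportion might be time-aligned, but with no stated time point this cannot be assumed.

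On direction, the label deterioration shows the intent, and D10 may be meant only for scales where higher is better. The text does not say so.

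**Conclusion.** The concern holds as a minor to moderate point. The HRQoL scores compare the arms over windows set by treatment length, and nothing time-aligned stands beside them. With no treatment effect, D10-DT shows about 4 to 5.5 points against marizomib under the simplest assumptions and 2.5 to 3 with correlated forms. It is near 1 or zero under early stopping of all drugs or TMZ extension, and about −3 in one long-term scenario; D10-AT shifts 2 to 3 points against control. Neither the size nor the sign is fixed, because both rest on assumed PFS, per-form risk, correlation, accrual and stopping patterns. AC-DT bias is about 1 point or less on a 0–100 scale.

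The D10 direction problem rests on the text alone up to one inference, that higher is worse on the three symptom-type scales. Read literally, the rule would then report the wrong direction there. No confirmatory claim depends on either issue.

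**What to change.** (a) Define D10 as a worsening of at least 10 points, with the direction stated per scale and checked against the scoring manuals, or limit it to the global and functional scales. Report it as a proportion with a risk difference; the planned mean difference of a 0/1 variable is already that quantity. Note the clarification against protocol 10.5.2, which carries the same wording.

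(b) Keep AC-DT and AC-AT. Add a supportive between-arm comparison of scores and of D10 by time since randomisation, over one common window whatever the treatment status, for example a baseline-adjusted repeated-measures model. Say that it answers a different question, because it includes off-treatment and post-progression forms. Label it as added after results were disclosed (SAP 2). State the window for each report: under the accrual assumed above, about 67%, 46% and 32% of the 616 patients could by calendar time have reached weeks 26, 42 and 58 at the cut-off.

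(c) State the time point of the responder proportion in SAP 13.6.1.

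(d) Before relying on post-progression forms, reconcile the protocol summary, which ends HRQoL collection at the start of new anticancer treatment, with protocol 6.3.2.2 and SAP 13.5, which continue it until death.

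The cost is some SAP wording and a little programming. No new data collection is needed, provided that (d) confirms the later forms exist.

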### 10.5.1 Primary analysis

The following statistical tests will be done corresponding to the objective listed in section 10.2.

The following two summary scores will be calculated per subject for each selected scale:

- the average change during treatment (AC-DT) = the average of all post-baseline scale scores up to and including the end-of-treatment visit (section 6.3.1) minus the score at baseline. Only scores from valid HRQoL forms will be included.
- the average change after treatment (AC-AT): = the average of all post-baseline scale scores during follow-up (i.e. after the end-of-treatment visit (section 6.3.1)) minus the score at baseline. Only scores from valid HRQoL forms will be included.

Description of the AC-DT and AC-AT will be presented (mean, standard deviation, median, first and third quartiles, minimum, maximum) by treatment group together with mean difference, 95% CI and the non-parametric test p-value (Wilcoxon).

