5.3. Stratification, Randomization, and Blinding

Subjects were centrally randomized in a 1:1 ratio using the multidimensional dynamic allocation algorithm from Medidata BALANCE module.

Medidata Balance uses a multidimensional Dynamic Allocation algorithm that minimizes imbalances across multiple dimensions including overall study, sites, factors and cross-factor strata. Like other dynamic allocation methods, it contains:

- An imbalance measure expressing the distance between the target treatment allocation and an allocation of treatments within a subgroup of subjects.
- A scoring system to summarize and prioritize the treatment imbalances over all subgroups of subjects (e.g. over sites, randomization factors, strata, etc.).
- A selection method to assign a treatment to the next subject which will minimize the total imbalance score.

Subjects who are eligible were randomized according to the following stratification factors:

- Institution,
- Age (≤ 55 , > 55 years),
- Karnofsky performance status (70/80, 90/100),
- Extent of surgery (partial/biopsy, gross total).

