11.3.3. Mini Mental State Examination (MMSE)

The Mini Mental State Examination (MMSE) is a brief, standardized tool to grade subjects' neurocognitive function. It is an 11-question measure that tests five areas of neurocognitive function: orientation, registration, attention and calculation, recall, and language. The maximum score is 30 which corresponds to the best neurocognitive function. Following Brown et al. (Brown PD, 2003), the subject's neurocognitive function will be considered 'impaired' if the MMSE score is 26 or less and 'normal' if it is 27 or more. Since its creation in 1975 by Folstein et al. (Folstein MF, 1975), the MMSE has been validated and extensively used in both clinical practice and research. Following Tangalos et al. (Tagalos EG, 1996) and as previously used by Brown et al., a decline of more than 3 points in the MMSE score will be considered to represent clinically significant deterioration. In this study, MMSE will be collected up to progression.

The evolution of MMSE over time will be interpreted at 2-sided significance level $\alpha=0.05$ for exploratory purpose taking into account the attrition as a result of subjects assessed only until progression. All MMSE results will thus be conditional on the subjects being otherwise free of progression. The distribution of the MMSE at each time point of evaluation will be described on the two treatment arms separately using means and their associated standard error (a graphical display will be considered). Median and range will also be provided. The proportion of subjects with 'normal' and 'impaired' MMSE score at baseline and at key timepoints of evaluation (e.g., baseline, at end of radiation therapy and then every 16 weeks) will also be displayed.

Linear mixed models with treatment, a (linear) time effect, a time-treatment interaction as fixed effects and subject specific random effect is fitted. The covariance structure which minimizes Akaike Information Criteria (AIC) will be used.

Longitudinal plots of mean MMSE score and 95% confidence interval based on Least Square Means from the linear mixed model will be presented over all assessment times by treatment group.

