13.6. Statistical Considerations

The primary HRQoL endpoint that is considered relevant for this study is the Global health/QoL status scale of the QLQ-C30 instrument. The secondary HRQoL endpoints will be the fatigue, physical function, neurocognitive function, communication and motor dysfunction scales. Other scales from QLQ-C30 and QLQ-BN20 will be analyzed on an exploratory basis. The “financial difficulties” scale of the QLQ-C30 will not be analyzed at all.

The sample size calculation has been performed based on OS data. This is the primary endpoint and therefore no calculation has been performed based on changes in HRQoL. The primary HRQoL endpoints that are considered relevant to this trial are detailed above. The HRQoL data will give information to support or reject the null hypothesis that there is no difference between patients in both arms during and after treatment.

Data will be scored according to the algorithm described in the EORTC scoring manuals for the corresponding instruments. All scales and single items are scored on categorical scales and linearly converted to 0-100 scales.

Primary and sensitivity analyses will be performed in the ITT population and in the uMGMT stratum.

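### The primary HRQoL comparison is an unadjusted difference in mean change scores, so its confidence interval is wider than it would be with adjustment for baseline and the randomisation factors

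*SAP*

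**What the plan says.** SAP 13.6.1 defines AC-DT as "the average of all post-baseline scale scores up to and including the end-of-treatment visit minus the score at baseline". AC-AT is built the same way from forms completed after the end-of-treatment visit. The SAP then says: "The mean difference between the two treatment arms for AC-DT and for AC-AT with corresponding 2-sided 95% CI will be derived". The interval is to be "contrasted with the 0 (no treatment arm difference) and the clinically important difference (CID) threshold". No model, covariate or stratum is named. Protocol 10.5.1 presents the same summaries by arm "together with mean difference, 95% CI and the non-parametric test p-value (Wilcoxon", also without covariates.

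No other section supplies an adjusted version:

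- SAP 6.1 applies the stratification factors to the stratified primary efficacy analyses and does not mention HRQoL.
- SAP 13.6.2 repeats the analysis in other populations and form sets and adds the binary D10 variables.
- The model building in SAP 13.6.3 concerns compliance, not the treatment effect.

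On allocation, SAP 5.3 says: "Subjects were centrally randomized in a 1:1 ratio using the multidimensional dynamic allocation algorithm from Medidata BALANCE module". The factors listed there are institution, age group, Karnofsky group and extent of surgery. All except institution are used for overall survival (SAP 11.2), PFS (SAP 11.3.1) and response (SAP 11.3.2).

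**The concern.** In a randomised comparison, the raw difference in mean change and the baseline-adjusted difference estimate the same quantity, but not with the same precision. A change score forces the coefficient on baseline to be 1, whereas a regression estimates it. Unless the true slope is 1, the change score leaves variance in the comparison that the baseline form could have removed. The factors used to balance the arms are also set aside for HRQoL, and no reason is given for treating it differently from the other endpoints.

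The interval is the tool for reading this endpoint. SAP 13.1 says that any survival gain must be balanced against the burden of treatment, and SAP 2 reports that the IDMC saw severe neurological and neuropsychiatric disorders with marizomib. Avoidable width makes it harder to show that HRQoL was harmed, and equally harder to rule out harm as large as the clinically important difference.

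**Working it through.** **Inputs from the documents.** Allocation is 1:1 (SAP 5.3). The interval is two-sided 95% (SAP 13.6.1). Total randomised is 749, about 374 per arm (SAP 2). The main HRQoL analysis is replaced by an exploratory one if compliance is below 70% (SAP 13.6.3). There is no planned HRQoL precision to reproduce, since "no calculation has been performed based on changes in HRQoL" (SAP 13.6).

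**Assumptions.** The baseline and post-baseline scores have a common SD s and a common correlation r, and each patient has m post-baseline forms. The documents give none of these values, so ranges are shown.

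**Formulas.** Per patient, in units of s²:

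- Average of m post-baseline scores: V = [1 + (m−1)r]/m
- Change score: V + 1 − 2r
- Baseline-adjusted: V − r²
- Excess of the change score: (V + 1 − 2r) − (V − r²) = (1−r)²

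The excess is never negative and is zero only at r = 1. The direction therefore does not depend on the value assumed for r; the size does.

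**Baseline adjustment alone.** Narrowing is 1 − √(adjusted variance / change-score variance) and does not depend on the number of patients.

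| m | r | Change score | Adjusted | CI narrower by |
|---|---|---|---|---|
| 1 | 0.3 | 1.40 | 0.91 | 19% |
| 1 | 0.5 | 1.00 | 0.75 | 13% |
| 1 | 0.7 | 0.60 | 0.51 | 8% |
| 2 | 0.3 | 1.05 | 0.56 | 27% |
| 2 | 0.5 | 0.75 | 0.50 | 18% |
| 2 | 0.7 | 0.45 | 0.36 | 11% |

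**In score points.** Half-width = 1.96 × s × √(2 × variance / n per arm). For illustration take s = 25 (assumed), m = 3, and n = 0.70 × 374 ≈ 262 per arm:

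- r = 0.5: 1.96 × 25 × √(2 × 0.667/262) = 3.50 unadjusted; with 0.417 in place of 0.667, 2.76 adjusted.
- r = 0.7: with 0.400 and 0.310, 2.71 unadjusted and 2.38 adjusted.

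**Randomisation factors.** If the three factors explained 5% or 10% of the variance left after baseline, the interval would narrow by a further 1 − √0.95 = 2.5% or 1 − √0.90 = 5.1%.

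**Simulation check.** The settings were 2,000 replicates, simple rather than dynamic allocation, 262 per arm, s = 22, m = 3, r = 0.5, and factors explaining 5% of score variance. Mean full interval width was 6.15 unadjusted, 4.87 with baseline, and 4.80 with baseline and the three factors. Coverage was 95.1% unadjusted and 95.3% with full adjustment. Baseline supplied nearly all the gain, and under simple allocation what was lost was precision, not validity.

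**The case against.** The case for leaving the plan alone has four parts.

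1. **Baseline is already used.** This is correct. A reader might infer that the plan ignores baseline, or that subtracting it adds its whole noise. Neither holds. Relative to comparing follow-up scores alone, subtraction adds 1 − 2r, which is zero at r = 0.5 and negative above. At m = 2 and r = 0.7 it cuts the variance from 0.85 to 0.45. The loss is only relative to an estimated coefficient.

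2. **The gain is small in points.** In the example above it is 0.74 points at r = 0.5 and 0.33 at r = 0.7, on a 0–100 scale where SAP 13.6.2 uses a 10-point deterioration rule. That the gain may be modest stands. However, the 10-point rule classifies individual patients, whereas the interval is read against a threshold for the difference between arm means. The SAP takes that threshold from a cited paper and does not print its value.

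3. **The endpoint is exploratory.** Protocol 10.5 calls the reporting mainly descriptive, and SAP 11.1 places every endpoint other than overall survival at an exploratory 5% level. This stands and limits the importance of the point. Even so, SAP 13.2 sets a null hypothesis for global HRQoL, and SAP 13.6.1 reads the interval against two reference values.

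4. **Missing data are the larger threat.** This also stands. Dropout and death, especially for AC-AT, are not cured by covariate adjustment.

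A reader might also infer that the unadjusted interval has materially wrong coverage because allocation balanced on these factors. Leaving out balancing factors tends, if anything, to make an interval conservative. How far depends on how much of the *change* they explain. If they shift baseline and follow-up equally, subtraction removes them. The documents give no basis for a figure.

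**Conclusion.** The point holds as a matter of precision. The comparison in SAP 13.6.1 and Protocol 10.5.1 is not biased by the lack of adjustment, but its interval is wider than the trial's own data allow. The excess variance is s²(1−r)². For assumed r of 0.3 to 0.7, adjusting for baseline narrows the interval by about 27% to 11% with two post-baseline forms and by about 19% to 8% with one. The randomisation factors add less, depending on how well they predict the score.

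The direction follows from the algebra under equal SDs and 1:1 allocation. The size rests on assumed correlations and numbers of forms and cannot be computed from the documents.

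Two wider readings are not supported. The conclusion does not carry over to the MMSE analysis in SAP 11.3.3 ("Linear mixed models with treatment, a (linear) time effect, a time-treatment interaction as fixed effects"): that is a different model with a subject random effect, and the change-score algebra does not apply to it. Nor does it touch the overall survival conclusion, since HRQoL is outside the error-controlled tests.

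**What to change.** In SAP 13.6.1, estimate the arm difference in AC-DT and AC-AT by a linear model (analysis of covariance) with treatment, baseline score, age group, Karnofsky group and extent of surgery. Take the factor values from the randomisation system, as SAP 11 does for the stratified tests. Report the adjusted difference with its two-sided 95% CI against the same thresholds. Carry the model through the repeats in SAP 13.6.2, and keep the unadjusted difference and the descriptive table as supportive. Record the departure from Protocol 10.5.1.

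SAP 3 places the HRQoL section in both the primary and the long-term follow-up reports, and Protocol 8.4 runs the follow-up analysis under an updated SAP, so there is a place to make the change. For any HRQoL results already known, label the adjusted version post hoc.

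The cost is a few sentences of SAP text and modest programming. All covariates are already collected, and the definitions of AC-DT and AC-AT already require a baseline score, so no further patients are lost.
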